Research support: [name], Research Radiographer, Radiology Department, Mid Yorkshire Hospitals NHS Trust (MYHT)

3 | Page

A pilot study to compare supine and erect pelvis radiographs – assessment of impact on radiation dose and diagnostic markers (SEPRAIDD)

Summary

X-ray images are a primary tool in investigating diseases of the hip joint. The reproducibility of this examination is especially important for diagnosis and monitoring of arthritis and following hip replacement surgery. Pelvis x-rays are routinely performed with the patient lying down, however some studies have shown that standing is more effective, demonstrating abnormalities taking into consideration the effect of load. Previous research has demonstrated that the pelvis tilts with different postures (i.e. lying, sitting, standing) and understanding these changes to the resultant x-ray image is vital. Importantly, no research has considered the radiation dose implications of changing from supine to standing technique.

This pilot study will examine differences in diagnostic markers and radiation dose between the different positions in three phases. To estimate the change in patient soft tissue anatomy between supine and erect positions in phase one we will recruit 180 patients referred for pelvis or hip radiographs to have their height, weight and trunk diameter/circumference measured whilst erect and supine. This data will allow modelling of the change in patient body shape between the two projections. For phase two an anthropomorphic phantom will then be utilised to establish the imaging protocol to provide suitable quality images with the lowest radiation dose. The third phase of the study will then recruit 60 patients who have been referred for pelvis or hip x-rays and they will have their imaging performed in **both** lying and standing positions. The recruitment and refusal rates will inform future study design and confirm sample size. The data will assist in determining variation in radiation dose, anatomical measures for hip disease and anatomy between positions.

A key outcome will be a grant application to determine if patient posture affects the clinical outcomes, in terms of image quality, or the radiation dose received by the patient. The outcomes from this study will support the development of future research which will seek to identify the clinical impact of erect pelvic radiographs in a large scale population.

Protocol: Supine and erect pelvis radiographs: A pilot study

4 | Page

Background

When evaluating diseases of the hip, clinical history and physical examination are commonly supplemented with radiographic images. Radiography is an essential tool in diagnosis of hip pathologies and is accessible, cheap and results in a relatively low radiation dose being delivered to the patient. Hip radiographs allow the evaluation of abnormal hip anatomy (dysplasia) and pathologies throughout the age spectrum. Hip pain in the younger adult is often related to dysplasia and pain can be symptomatic of impingement. However, it is the evaluation and monitoring of osteoarthritis (OA) which accounts for the greatest utilisation of radiography in the non-trauma setting. As the hip is subject to ongoing wear and tear² OA largely affects older people and by 2020 it will be the fourth most common cause of disability in the UK.³ It is estimated that hip OA is symptomatic in 5-9% of the population, with pain, stiffness, deformity and/or decreased mobility. It has a poor outcome, with a significant number progressing to joint replacement within 5 years. Not all patients with radiographic evidence of OA, likely to be as high as 19%, will have symptoms but it is suggested that half will be suffering. Radiographs also support surgical planning, with a need to accurately template anatomy to ensure correct choice of components and location⁵. Siting a replacement within a suboptimal location can increase the risk of dislocation and failure. For these patients ongoing monitoring is required and radiography is performed on a regular basis to check for signs of loosening and failure.

Radiographic diagnosis relies on the identification of often subtle changes but these may be masked by variations in hip alignment as a result of patient positioning^{6,7} or anatomical variations which may cause apparent, or true, pelvic anteversion (anterior tilt) or retroversion (posterior tilt).^{8,9} Siebenrock et al¹⁰ suggested limits for neutral radiographic pelvic tilt to ensure acceptability, but they did not acknowledge natural variations between persons, but rather took it as a failure of radiographer positioning.

Hip radiographs are traditionally performed with the patient supine, however an assessment of anatomical relationships is required to diagnose and treat musculoskeletal disorders on an individual basis. ^{6,11} As the hip carries the weight of the body there is potential for these relationships to vary with an erect posture. This has significant relevance with increasing obesity which is known to alter posture. Therefore conforming investigations to potential causality for, or exacerbation of, pain and/or presentation is important. It has been confirmed that pelvic orientation changes between lying, sitting and standing with the pelvis tilting with upright posture. A review by Troelsen ⁶ found that changes varied from nil to 8°. Importantly, research studies cannot be compared directly due to variations in population (normal subjects or dysplasia) and measures (AP and/or lateral radiographs or inclinometer). The work by Troelsen confirmed that the change in pelvic tilt can vary between females (13-14°) and males (6-7°). The consensus is therefore strong that there is a change in pelvic orientation related to posture and that this change may have significant implications for stability of hip replacements and exacerbation of pain in patients with impingement or OA.

This recognition has led to a number of authors to suggest that radiography should be obtained erect, as pain is often only present during weightbearing.^{2,6,12,13} This integrates radiographic technique with symptoms, function and potential hip deformity or pathology. Previous research has predominantly been led by orthopaedic surgeons and has considered the impact of patient

orientation to pelvic tilt, ^{11,12,13} hip joint space width ^{7,14,15} or postoperative acetabular version. ^{5,16,17} Research is severely limited in sample size and has focused on specific patient groups rather than the broader population. Importantly the result of previous research are inconsistent and studies have found the hip joint space to be reduced or unchanged. ¹⁵ This therefore presents a limited and conflicting evidence base, with no agreed parameters for positioning.

The inconsistent radiographic technique and centring points have also been highlighted by patient exclusions in orthopaedic research studies because radiographs do not meet pre-determined positional and quality criteria. Interestingly, issues of radiographic technique were also identified in the 2014 NICE guidelines for hip OA³ which states that differing radiographic protocols contribute to a lack of robust evidence around their use. Radiography textbooks are also contradictory, resulting in local variation. Indeed one textbook suggests flexing a patients' hips and knees slightly to correct for pelvic tilt, a factor unlikely to be appreciated by clinicians, with potential to lead to misinterpretation.

Importantly, no previous study has considered the radiation dose implications of patient posture or defined the standardised positioning required to introduce this as a mainstream investigation. Patient position has potential to influence radiation dose through reduced soft-tissue compression and increased overlying abdominal tissues. This would have significant implications for image quality, which in turn could impact on clinical decision making. National dose reference levels (DRLs) do not exist for erect positioning, a non-standard technique, meaning that there is no parameters for dose in this projection, despite a small number of Trusts already adopting this technique. Interestingly, authors have demonstrated opportunities to reduce radiation dose with increased distance or orientation on digital equipment, but these were only undertaken supine using an anthropomorphic phantom^{24,25,26} and have not been translated into clinical practice. As a result this research hopes to develop a patient centred evidence base for the positioning and exposure factors for erect AP pelvis projections.

Key research questions

The key research questions requiring an answer are:

- 1. Does pelvic radiography performed in the erect position result in an increase in radiation dose to the patient?
- 2. Does pelvic radiography performed in the erect position demonstrate clinically significant changes in image quality when compared to a supine X-ray image?
- 3. Are erect pelvic radiographs acceptable to patients in their performance?
- 4. Would the change impact on service delivery, in terms of examination time?

Aims

This study aims to ensure that X-ray images of the pelvis are performed using evidence based protocols. It will also determine if patient posture (erect or supine) has an effect on radiation dose, image quality and diagnostic measures.

[figure not shown]
The study objectives are to:

- Develop trial procedures, imaging protocols and patient information for a future study
- Estimate the recruitment rate for a prospective study which will the diagnostic and dose differences between supine and erect pelvic radiographs
- Identify the recruitment and refusal rates to such research.

Study site

A single NHS Trust is being used to control for variations in technique and equipment. Mid Yorkshire Hospitals NHS Trust (MYH) comprises 3 hospital sites, Dewsbury District Hospital, Pinderfields Hospital (Wakefield) and Pontefract Hospital. Almost 8000 adult patients were referred from either their GP or as an outpatient to the Trust radiology department for pelvis or hip radiographs in 2016, including those referred for a hip x-ray where a full pelvic radiograph is performed as standard. The age profile of these patients is demonstrated in Figure 1. This demonstrates that the median age of this patient population is 65, with 80% of all patients being over 50 years in age.

Method

Phase One: Patient modelling

The initial data collection will focus on ascertaining the patient population and how physical characteristics (body shape) differs between the erect and supine positions. This will be through standardised measures obtained in both positions.

Sample size

A cohort of 180 patients who are attending for radiography of the hip or pelvis from either an outpatient (OP) clinic or their general practitioner (GP) will be recruited. Specifically the study aims to achieve a minimum of 30 patients in each of the following categories:

Underweight/Normal (BMI<25)

Overweight (BMI 25-30)

Obese/Morbidly obese (BMI>30)

Inclusion criteria

All patients who attend for radiographs of the hip or pelvis from a MYH OP clinic or their GP will be eligible for inclusion to the study. It is estimated that there are approximately 60 eligible patients per week attending each hospital site within the study organisation.

Exclusion criteria

Patients who are under the age of 18, pregnant, are unable to stand unaided, have undergone lower limb surgery within the previous six months or are unable to provide written informed consent will be excluded from the study. A further exclusion will be related to patients who are unable to stand unaided, as the ability to weight bear would be a key component in performance of an x-ray in the erect posture.

Withdrawal

Any participant can withdraw from the study at any point prior to final data analysis, expected to be 1 month from end of recruitment. Their data will be excluded from the study and records destroyed, however the radiographs will be retained as part of the clinical record.

Recruitment process

Recruitment will take place over a 6-week period to allow for workflow variation and patient refusal. Reasons for patient refusal will be collated to inform a future trial.

A study patient information leaflet (Appendix 1) will be sent with appointment letters for potential recruits from the general practitioner. These patients will be identified by the radiology appointments team at the time of booking an examination. This will also be made available within the orthopaedic clinic to patients attending for an appointment. The information sheet will explain what the study is undertaking and what the research is looking at and explain the risks and benefits of taking part. This will allow time for potential recruits to read the patient information leaflet and, if required, approach the study team prior to being asked for informed consent.

Poster information will also be displayed within the hospital outpatient areas for patients to read prior to attending the radiology department.

When the patient attends the radiology department for their radiographs a member of the radiology team will confirm their eligibility to participate in the study. A GCP trained member of staff who is a fully qualified radiographer who works permanently within the radiology department will then approach the patient, introduce themselves and explain the study and research and what will be required from them to take part within the study. Informed written consent (Appendix 2) will then be gathered from each recruit prior to any data collection.

Data collection

The recruited participant will be asked to change into a gown appropriate to their radiological examination and then taken to a private room (x-ray room) to maintain dignity and privacy. They will then have various measures undertaken by the research team member (see instruction sheet appendix 3).

These will include:

- Height (m)
- Weight (kg)
- Body circumference
- Source-Object Distance (i.e. x-ray tube to patient skin, as a proxy for body diameter)

A small group of radiographers will be trained to undertake the specific study parameters to ensure consistent data collection (Appendix 4). They will then continue with the radiographic examination as requested by the referring clinician.

Data analysis

The data collected will allow modelling of the change in patient body shape between the two projections. Variations in shape between BMI subgroup, gender and age will be assessed. Mean and standard deviations will be calculated if the resultant data are approximately normally distributed and median (ISR) measures will be determined for non-parametric data.

[figure not shown]
Phase Two: Phantom Experiment

An anthropomorphic phantom of the abdomen and pelvis will be used to investigate the optimal image acquisition protocol based on the anatomical changes identified in phase one. No patients will be recruited for this part of the study.

The outcome of the phantom study will be specific kV and mAs settings or automatic exposure control (AEC) settings for the different techniques and comparison of the phantom dose data with national diagnostic reference levels.

Based on the variation in mean measures between the different position and body habitus in phase one a Kyoto phantom will be physically altered with the addition of appropriately positioned soft tissue density mimicking material. This will enable multiple exposures of the phantom to be made at different distances and exposure factors to ascertain whether automatic exposure devices can be reliably used in both of the patient positions or whether specific exposure charts should be calculated regarding a patient's body habitus.

An example of the acquisition procedure is demonstrated in figure 2 below. The resultant images will be analysed for quality in relation to visualisation of the bony anatomy of the pelvis and hip joint. Based on a previously validated technique²⁶ radiation dose (entrance surface dose (ESD) and effective dose (ED)) will be calculated using a commercially available computer software system which utilises Monte Carlo code dose simulation (PCMXC). Calculations require the source-object distance, mAs and peak tube potential values (kV) to be entered for each data point.

Phase Three: Pelvic Radiograph Acquisition

This phase will compare radiographs obtained on the same patient in two different positions, supine and erect. The supine positioning is that which is currently undertaken within the imaging department. The erect positioning technique and acquisition parameters will be informed by the earlier phases of the research.

Sample size

A single arm pilot study is planned with no attempt at this time to undertake sub-group analysis. A minimum of sixty patients will be recruited to this study based on the premise of the future trial demonstrating a 5% difference in pelvic tilt between the 2 projections (95% confidence interval), ²⁷ this exceeds 10% of the potential future trial requirements ^{28,29} and includes a minimum of 12 participants per subgroup. ³⁰

The future trial is estimated to require a minimum sample of 474, based on the same calculations. To allow for the inability to perform the erect x-ray, exclusion based on image quality and to enable sub-group analysis, it is planned that the sample recruited would be 800. The subgroup analysis for referral reason will comprise:

- 1. Young adult with hip pain (18-40)
- 2. Patient with evidence of hip dysplasia
- 3. Older adult referred with symptoms or diagnosis of OA
- 4. Previous hip replacement under monitoring

Inclusion criteria

All patients who attend for general radiography of the hip or pelvis from their general practitioner or outpatient clinic will be eligible for inclusion to the study. It is estimated that there are approximately 60 eligible patients per week attending any one hospital site within the study organisation.

Exclusion criteria

Patients who are under the age of 18, pregnant, have recent trauma or undergone hip or knee surgery within the previous six months or are unable to provide written informed consent will be excluded from the study. Patients who have a pelvic x-ray or pelvic radiotherapy in the preceding 6 months will also be excluded to minimise their radiation exposure. A further exclusion will be related to patients who are unable to stand unaided, as the ability to weight bear is a key component in performance of an x-ray in the erect posture.

Recruitment process

A phase three study patient information leaflet (Appendix 5) will be sent with appointment letters for potential recruits from the general practitioner. These patients will be identified by the radiology appointments team at the time of booking an examination. The information sheet will introduce the study and what the research is looking at and explain the risks and benefits of taking part. This will allow time for potential recruits to read the patient information leaflet and, if required, discuss with family or friends or approach the study team prior to being asked for informed consent.

Poster information will also be displayed within the hospital outpatient areas for patients to read prior to attending the radiology department.

When the patient attends the radiology department for their radiographs a member of the radiology team will confirm their eligibility to participate in the study. A GCP trained member of staff (HCPC registered radiographer who works permanently within the radiology department will then approach the patient, introduce themselves, explain the study and research and what will be required from them to take part within the study. Informed written consent will be gathered from each recruit prior to undertaking their radiographic examination (Appendix 6).

Any participant can withdraw from the study at any point prior to final data analysis, expected to start 1 month following the last recruit. Their data will be excluded from the study and study records destroyed. The radiographs obtained will be retained as part of their personal clinical record.

Study procedures

Imaging will be performed by specific study radiographers who will have received specialised training in undertaking pelvic radiography in the erect position. The training will be led by the study investigators, experienced radiographers with additional qualifications in image reporting.

Each patient will be radiographed in two positions, supine with a SID of 115 cm (current technique employed within the imaging department) and erect with a SID of 180cm (new comparison technique). Additionally the patient will have their height and weight measured to confirm the appropriate exposure parameters established in phase two.

The supine and erect radiographic examinations will be performed in a random order with the preprinted data collection sheets indicating the order of the patient. This will be established using a random number generator. This procedure ensures that the patient preference cannot be related to the examination order.

Data collection and management

A data collection sheet will be used to record information about each study participant and the imaging parameters (Appendix 7). The data includes the anatomical measures (phase one and three) and exposure parameters (phase three only) and the patient will be asked their preference for the imaging technique (erect or supine). The data will be transcribed as soon as practicable into the Trust research management system EDGE with patient identifiable data being removed.

The additional erect pelvis projection will be stored on the MYT PACS system. Additionally anonymised copied will be stored to a study teaching file on PACS using their unique study identifier to allow blinded image review. The PI is a PACS administrator and will ensure this data is securely managed.

On completion of the recruitment data validation will take place to ensure there are no transcription errors and missing data. The final data set will be exported into Microsoft Excel for analysis. Further statistical analysis will take place using PCMXC and SPSS.

Data analysis

The phase three data will allow the comparison of the radiation dose (entrance surface dose (ESD) and effective dose (ED)) will be calculated using a commercially available computer software system which utilises Monte Carlo code dose simulation (PCMXC). Calculations will use the source-object distance, mAs and peak tube potential values (kV) for each exposure.

Descriptive analysis of the participant demographics and the image acquisition parameters will be undertaken, including patient preference and thematic analysis of any free text comments from the radiographer or patient. Comparison of examination length will be undertaken utilising the 'start time' and the time on the last image in that orientation, it is acknowledged this outcome will be influenced by the need for repeat exposures and technical difficulties in this small cohort.

Initial image quality will be assessed in relation to the diagnostic value of the radiograph and whether a repeat x-ray would have been warranted, this will allow comparison of repeat rates for the 2 examinations as well as the reasons. Further assessment of image quality will use a previously validated psychometric scale³¹ to compare the noise at different anatomical regions. This will provide a comparison between the 2 projections, the images will be randomly allocated for analysis and reviewers will be blinded to the acquisition technique (erect or supine) for this analysis to reduce bias and maintain objectivity.

Ethical Consideration

The key ethical issue associated with this research is the requirement for an additional x-ray in phase three. Other options have been explored including using only an anthropomorphic phantom and randomization of patients to either examination. These strategies do not provide sufficient robustness to demonstrate changes on an individual basis and the phantoms have fixed bony and soft tissue anatomy and therefore do not allow comparison of changes related to posture.

REC and HRA approval will be sought to ensure the additional radiation dose is managed within an appropriate framework. This will include establishing protocols to limit radiation exposure through exclusion from the study if repeat x-rays are required due to quality reasons. A patient will only have one radiograph taken in the erect position, regardless of final image appearances. This will ensure that the maximum additional dose for a single patient is limited to one exposure whilst maintaining the integrity of their clinical examination. This will also provide information regarding the potential repeat rate for erect radiographs in a prospective future trial. The study team will then decide whether the patient is excluded from the study, included for limited analysis or fully included despite imaging appearances, on a case by case basis.

The number of radiographers able to obtain study images will be limited to provide quality assurance with the erect technique which is non-standard. These will undergo training and images will be assessed for quality throughout the study, providing opportunity for interventions if any variation from the protocol is identified.

Additional radiation dose reduction techniques will be adopted and these will be optimised during phase two of the study. Monitoring of patient radiation dose will be paramount, as with any imaging

study. A dose constraint will be established prior to ethical approval in line with the Ionising Radiation (Medical Exposure) Regulations 2000 (IRMER), if it is identified that certain patient groups are approaching this constraint a decision will be made to limit recruitment.

Patients will be informed of the study in advance, either with their radiology appointment letter or with clinic information depending on referral route. In addition posters will be distributed to GP surgeries and OP clinics to raise awareness. Patients will be provided information leaflets and the opportunity to discuss the study prior to the consent process.

Participants will be consented to the measures (and additional x-ray – phase 3 only) and will be able to withdraw their consent at any time during the radiology appointment without detriment to their care. Patients will be consented at time of their x-ray but will be given the chance to withdraw their data up to the start of data analysis, which is expected to be up to one month from end of recruitment. This information will be provided to patients. Permission to perform the additional measures (and x-ray) will be obtained in private prior to the examination within the radiology department. Confidentiality of participants will be maintained and the processes for data management will be compliant with the Data Protection Act (1998).

Source data, consent forms and patient screening questionnaires will be stored in a locked filing cabinet within a locked research office. Data transfer will be by encrypted Trust devices. Only the research team will have access to this data. All reports and dissemination of findings will only include anonymised data.

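### Diagnostic measures are a stated aim and a pelvic tilt difference is the sample size premise, yet phase three plans no radiographic marker measurement or supine-erect marker comparison

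*Protocol*

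**What the plan says.** All references are to the Protocol.

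**What is promised**
- The title names diagnostic markers next to radiation dose. The Summary repeats this: "This pilot study will examine differences in diagnostic markers and radiation dose between the different positions in three phases".
- At the end of its account of phase three, the Summary says: "The data will assist in determining variation in radiation dose, anatomical measures for hip disease and anatomy between positions".
- Aims: "It will also determine if patient posture (erect or supine) has an effect on radiation dose, image quality and diagnostic measures". Diagnostic measures stand there as an item separate from image quality.
- Phase Three, Sample size: "A minimum of sixty patients will be recruited to this study", on the premise of a future trial "demonstrating a 5% difference in pelvic tilt between the 2 projections". The future minimum of 474 is said to come from the same calculations.

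**What is planned for phase three**
- Data collection and management lists anatomical measures for phases one and three, exposure parameters and patient preference. Anonymised copies of the images are stored for blinded review.
- Data analysis covers entrance surface dose and effective dose, demographics, acquisition parameters, preference, free-text comments, examination length, and diagnostic value with whether a repeat was warranted. It then adds: "Further assessment of image quality will use a previously validated psychometric scale", used to compare noise by anatomical region.
- Appendix 7 (phase three data sheet) has fields for identifiers, imaging order, height, weight, age, gender, kV, mAs, DAP, EI, times, repeat, comments, preference and radiographer code.

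The four Key research questions concern dose, image quality, acceptability to patients and examination time. None concerns a marker.

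**The concern.** A stated aim should lead to a named measurement, a place to record it and a planned comparison. The diagnostic-measures aim has none of these in phase three. Pelvic tilt, the quantity on which the sample size argument is built, is not an outcome of the study sized on it.

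Two things are at stake. First, if the protocol is followed as written, the study reports on dose, image quality, preference and timing but cannot answer its own aim on diagnostic measures. Second, the pilot returns nothing about tilt to the calculation for the future trial. The Summary says that recruitment and refusal rates will confirm the sample size. Those rates show whether a number can be recruited, not whether it suffices for a tilt difference.

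**Working it through.** **1. The plan's own figures.** The premise supplies 5% and 95%, but no SD, baseline tilt, power or sidedness.
- One pilot-size formula that uses only these two numbers is n = ln(1 − 0.95) / ln(1 − 0.05) = 58.4, rounded up to 59. This is within one patient of 60. That the authors used it is an assumption, and tilt does not enter it.
- The two supporting rules hold: 10% of 474 is 47.4, and 4 subgroups × 12 is 48. Both are below 60.
- 474 cannot be derived from the stated inputs. In a paired comparison (two-sided 5%, 80% power) it would correspond to a standardised difference of (1.960 + 0.842) / √474 = 0.129. The protocol gives no SD from which to judge that value.

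**2. Promise against plan.**
- *Diagnostic measures (Aims)*: the nearest analysis item is diagnostic value, which is tied to whether a repeat was warranted. It judges the adequacy of the image and measures no marker.
- *Anatomical measures for hip disease (Summary)*: the nearest item is the mention of anatomical measures under Data collection and management. In phase one these are height, weight, body circumference and source-object distance (Phase One, Data collection; Appendices 3 and 4). For phase three, Study procedures and Appendix 7 give only height and weight. The phrase therefore matches body measures, not measures read from a radiograph.
- *Pelvic tilt (Sample size)*: there is no measurement, method, reader or comparison in the phase three text.

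**3. What reading the stored images would give.** Inputs: n = 60 pairs (Sample size), all assumed readable, with roughly normal differences.
- Mean difference: 95% half-width = t(0.975, 59) / √60 = 2.001 / 7.746 = 0.258 SD.
- SD of the difference: √(59 / 82.12) = 0.848 to √(59 / 39.66) = 1.220 times the estimate.
- A paired sample size scales with SD², so that input would be known to 0.848² = 0.72 up to 1.220² = 1.49 times.
- With fewer readable pairs, precision falls slowly: 54 pairs give ±0.273 SD and 0.84 to 1.23 times; 48 pairs give ±0.290 SD and 0.83 to 1.25 times.

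**4. Why the SD is worth having.** Assume that the 5% is relative to mean tilt and that the analysis is paired, two-sided 5%, 80% power. Then n = [r × 2.802 / 0.05]², where r is the SD of the difference divided by the mean. The protocol gives no r, so a range is shown:

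| r | n |
|---|---|
| 0.10 | 32 |
| 0.20 | 126 |
| 0.39 | 478 |
| 0.50 | 785 |
| 1.0 | 3140 |

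**The case against.** The other side has several fair points.

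- **The listed questions are covered.** All four Key research questions have planned phase three data. The objectives concern procedures and recruitment, and place the diagnostic and dose differences in a prospective study. This stands, but it shows that the questions and the aim disagree. It does not supply the missing outcome.
- **Appendix 7 is weak evidence by itself.** It is an X-ray room sheet. It has no field for the image quality scores either, although these are clearly planned, nor for the source-object distance that the dose calculation uses. This stands. The point rests mainly on the analysis text, which names the image quality scale and no marker.
- **A SAP may hold the detail.** Marker definitions and reading forms could sit there. But the protocol sets out its own list of phase three measurements and analyses, and a stated aim is absent from that list. This is more than missing detail.
- **The protocol never promises an SD.** Correct. The need for one is inferred from the tilt premise.

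A reader might also infer stronger claims that the documents do not support:
- That tilt is in the title or aim. They speak of diagnostic markers and diagnostic measures; as a study quantity, tilt appears only in the sample size premise.
- That the data are lost. The paired images are retained.
- That the extra exposure yields nothing. It yields paired dose, image quality, preference and timing data.
- That the tilt SD is all the future sample size needs. The 474 cannot be traced to an SD, and the planned 800 also allows for failed erect images, quality exclusions and subgroups.

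**Conclusion.** The point holds as a mismatch inside the protocol. The title, Summary and Aims promise a supine-erect comparison of diagnostic or anatomical measures, and the sample size cites pelvic tilt, but phase three plans no marker measurement or comparison. As written, the number of planned paired marker measurements is zero. With all 60 pairs read, the study could report the mean tilt difference to about ±0.26 SD and its SD to 0.85 to 1.22 times the estimate. These figures assume roughly normal differences and full readability; the second assumption is optimistic, since only one erect exposure is allowed whatever its quality.

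The conclusion does not depend on how 60 or 474 was obtained. It should be settled before the phase three images are read, because the aim can still be met from images already planned.

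**What to change.** Add a short passage to the phase three Data analysis:

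- The blinded reviewers already planned measure pelvic tilt on both images of every patient with a readable pair, by one AP-radiograph method named in the protocol. The Background notes that earlier studies differ in how they measured tilt, so the method must be fixed.
- Readings go on a reader form kept separate from the X-ray room sheet.
- Report the number of readable pairs, the mean within-patient difference with its 95% CI, and the SD of that difference.
- Use that SD as one input when checking the future sample size, alongside recruitment, refusal and image failure rates.

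Add joint space width only if the information needed to correct for magnification is recorded. The two images use SIDs of 115 cm and 180 cm, and the phase three sheet holds neither an object-to-detector distance nor a calibration marker. The same caution applies if the chosen tilt method rests on a distance rather than an angle or ratio.

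The cost is extra reading time, a reading form and the choice of a method; no further imaging is needed. If the investigators do not want to measure a marker, the alternative is to remove the diagnostic-measures aim and the tilt premise, and to bring the title and Summary into line with the four Key research questions.
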